5.3. Lifestyle Considerations

Not applicable.

5.4. Screen Failures

Screen failures are defined as participants who consent to participate in the clinical study but are not subsequently enrolled into the study. A minimal set of screen failure information is required to ensure transparent reporting of screen failure participants to meet the Consolidated Standards of Reporting Trials publishing requirements and to respond to queries from regulatory authorities. Minimal information includes demography, screen failure details, eligibility criteria, and any SAEs.

Participants may be rescreened for the study if there is a change in their medical status that would affect their eligibility such as discontinuation of a prohibited medication or short intercurrent illness that has resolved. Clinical laboratory abnormalities detected at screening may be repeated as part of screening and should not be considered criteria for re-screening.

5.5. Replacement of Participants

No participants will be replaced at any time during this study.

6. STUDY TREATMENT

6.1. Study Treatment Administered

The study will use an IRT system for management of study enrollment. The system will assign the participant study number, track participant visits, and manage of study drug inventory. See Table 3 for study drug information.

Extension Period:

Participants will be dispensed the appropriate amount of study drug until their next scheduled visit. Participants will continue to self-administer INCB050465 per the investigator's instruction with study drug compliance continuing to be assessed.

Table 3: Study Drug Information

Study Drug Name:	INCB050465
Dosage Formulation:	Tablet
Unit Dose Strength(s)/Dosage Level(s):	1 mg and 2.5 mg
Route of Administration:	Oral
Administration Instructions:	1 tablet QD. INCB050465 will be taken orally with water without regard to food except on mornings of PK clinic visits (see Table 1 and Table 6). Participants should not take their dose at home when they have a PK visit. INCB050465 should be taken at approximately the same time each day.
Packaging and Labeling:	INCB050465 will be provided as 1 mg and 2.5 mg tablets packaged in high-density polyethylene bottles. No preparation is required. All Incyte investigational product labels will be in the local language and will comply with the legal requirements of each country.
Storage:	Bottles of INCB050465 should be stored at ambient conditions (15°C-30°C or 59°F-86°F).

6.2. Instruction to Participants for Handling Study Drug

Participants must be instructed in the handling of INCB050465 as follows:

- Store study drug at room temperature (15°C-30°C or 59°F-86°F).
- Only remove the number of tablets needed from the study drug bottle at the time of administration.
- Do not remove doses in advance of the next scheduled administration.
- Make every effort to take doses on schedule.
- Report any missed doses.
- Keep study drug in a safe place and out of reach of children.
- Bring all used and unused study drug bottles to the site at each visit.

6.3. Preparation, Handling, and Accountability

The investigator is responsible for drug accountability at the study site; however, some of the drug accountability duties may be assigned to an appropriate pharmacist or other designee. Inventory and accountability records must be maintained and readily available for inspection by the study monitor and are open to inspection at any time by any applicable regulatory authorities. The investigator or designee must maintain records that document:

- Delivery of study drug to the study site.
- Inventory of study drug at the site.
- Participant use of the study drug, including pill or unit counts from each supply dispensed.
- Return of study drug to the investigator or designee by participants.

The investigational product must be used only in accordance with the Protocol. The investigator will also maintain records adequately documenting that the participants were provided the specified study drug. These records should include dates, quantities, and any available batch or serial numbers or unique code numbers assigned to the investigational product and study participants.

Completed accountability records will be archived by the site. The investigator or designee will be expected to collect and retain all used, unused, and partially used containers of study drug until verified by the study monitor (unless otherwise agreed to by the sponsor). At the conclusion of the study, the investigator or designee will oversee shipment of any remaining study drug back to the sponsor or its designee for destruction according to institutional standard operating procedures. If local procedures mandate on-site destruction of investigational supply, the site should (where local procedures allow) maintain the investigational supply until the study monitor inspects the accountability records in order to evaluate compliance and accuracy of accountability by the investigative site. At sites where the study drug is destroyed before monitor inspection, the monitors rely on documentation of destruction per the site's standard operating procedure.

6.4. Measures to Minimize Bias: Randomization and Blinding

Not applicable.

6.5. Study Treatment Compliance

Compliance with all study-related treatments should be emphasized to the participant by the site personnel, and appropriate steps should be taken to optimize compliance during the study. Compliance with study drug will be calculated by the sponsor based on the drug accountability documented by the site staff and monitored by the sponsor/designee (tablet counts). Participants will be instructed to bring all study drugs with them to the study visits in order for site personnel to conduct tablet counts to assess study drug accountability. The drug accountability documentation will be used by the sponsor to calculate treatment compliance.

6.6. Dose Modifications

6.6.1. Criteria and Procedures for Dose Increases of Study Drug

At Week 6, participants may be eligible for a dose increase. Due to the need to receive clinical laboratory results and to consult with the sponsor as needed prior to increasing the dose, investigators may implement the dose increase either at an unscheduled drug dispensing visit between the Week 6 and Week 8 visits or at the scheduled Week 8 visit. Any other requests for dose increase at alternate times may be considered on an individual basis in consultation with the sponsor. Individual participants in Cohort 1 may increase from INCB050465 1 mg QD to 2.5 mg QD with sponsor preapproval in the following circumstances, provided that protocol eligibility criteria are met at the time of escalation:

- Dose increase criteria, defined as the following:
 - The participant continues to require transfusions by the Week 6 visit or
 - The participant does not attain a meaningful clinical response (at least a stabilization ≥ 2 g/dL increase in hemoglobin from baseline to Week 6).
- The investigator determines there has not been a clinically meaningful response in hemoglobin and other hemolysis parameters.
- The participant is otherwise tolerating the current dose and has not had any drug-related adverse events.
- In the opinion of the investigator, the participant does not have a concurrent condition or circumstance that would complicate the dose escalation or PK sampling, or pose an increased risk.

6.6.2. Criteria and Procedures for Dose Interruptions and Adjustments of Study Drug

Individual decisions regarding dose interruptions and reductions should be made using clinical judgment and in consultation with the sponsor's medical monitor, taking into account relatedness of the AE to the study drug and the participant's underlying condition.

In all cases, investigators may employ any measures or concomitant medications, after discussion with the sponsor (whenever possible), necessary to optimally treat the participant.

Adverse events that have a clear alternative explanation or transient (≤ 72 hours) or abnormal laboratory values without associated clinically significant signs or symptoms may be exempt from dose reduction guidelines. If there are any tolerability issues in individual participants who received 2.5 mg in Cohort 1, the dose may be decreased to 1 mg. For Cohort 2, dose reduction from 2.5 mg QD to 1 mg QD may occur if there are SAEs or AEs that are attributed to be related to INCB050465 (see Table 4 for the guidelines). Dose reduction may occur at any time during the 12 weeks of administration; however, consultation between the investigator and sponsor should occur if dose reduction is being considered for any participant.

Table 4: Guidelines for Interruption and Restarting of Study Drug

ADVERSE EVENT	ACTION TAKEN					
Chemistry						
AST and/or ALT is > 3.0 × ULN.	 Step 1: Interrupt study drug up to 2 weeks (14 days) until the toxicity has resolved to ≤ Grade 1 except by approval of the medical monitor. Step 2: Restart study drug at same dose. If assessed as related to study drug, restart study drug at 1 mg if receiving 2.5 mg and monitor as clinically indicated. 					
Hematology						
 ANC ≤ 1.0 × 10⁹/L, unless due to underlying disease. Platelet count is 50 × 10⁹/L to < 75 × 10⁹/L, unless due to underlying disease. 	 Step 1: Interrupt study drug up to 2 weeks (14 days) until the toxicity has resolved to ≤ Grade 1 or pretherapy baseline. Step 2: Restart study drug at same dose and monitor as clinically indicated. 					
 Grade 4 ANC (< 0.5 × 10⁹/L). ≥ Grade 3 ANC with an oral temperature of at least 38.5°C OR with ≥ Grade 3 infection. Platelet count is < 50 × 10⁹/L. 	Discontinue study drug administration and follow-up per Protocol. (Exceptions require approval of sponsor.)					
Other toxicities						
Any Grade 1 or Grade 2 toxicity.	Continue study drug administration and treat the toxicity; monitor as clinically indicated.					
Any Grade 3 toxicity, if clinically significant and not manageable by supportive care.	 Step 1: Interrupt study drug up to 2 weeks (14 days), until toxicity resolves to ≤ Grade 1. Step 2: Restart study drug at same dose. If assessed as related to study drug, restart study drug at 1 mg if receiving 2.5 mg and monitor as clinically indicated. 					
Any recurrent Grade 3 toxicity after dose reduction.	Discontinue study drug administration and follow-up per Protocol. (Exceptions require approval of sponsor.)					
Any other Grade 4 toxicity.	Discontinue study drug administration and follow-up per Protocol.					

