5.2. Exclusion Criteria

A participant who meets any of the following criteria will be excluded from the study:

- 1. Pregnant or breastfeeding women.
- 2. Concurrent conditions and history of other diseases:
 - a. History or clinical manifestations of significant unstable metabolic, hepatic, renal, hematological, pulmonary, cardiovascular, gastrointestinal, urological, neurological, or psychiatric disorders.
 - b. Current or previous malignancy within 5 years of study entry, except basal or squamous cell skin cancer with removal considered to be curative, superficial bladder cancer, prostate intraepithelial neoplasm, carcinoma in situ of the cervix, or other noninvasive or indolent malignancy without sponsor approval.
 - c. Clinically significant cardiac disease, including unstable angina, acute myocardial infarction, and or cardiac conduction issues within 6 months of the date of study drug administration.
 - d. Current New York Heart Association Class II to IV congestive heart failure or uncontrolled arrhythmia.
- 3. Inadequate hematologic function defined as follows (as determined by local laboratory):
 - a. ANC $< 1.5 \times 10^9 / L$.
 - b. Platelet count $< 100 \times 10^9/L$.
- 4. Severely impaired liver function (Child-Pugh Class C) or ALT or AST \geq 2 × ULN on repeated assessment.
- 5. Impaired renal function with estimated creatinine clearance less than 45 mL/min.

- 6. Anti-phospholipid antibodies positive or elevated anti-streptolysin antibodies.
- 7. Hepatitis B (HBV) or hepatitis C (HCV) infection: Participants who are positive for the hepatitis B surface antibody or hepatitis B core antibody will be eligible if they are negative for HBV-DNA; these participants should be considered for prophylactic antiviral therapy. Participants who are positive for the anti-HCV antibody will be eligible if they are negative for HCV-RNA.
- 8. Known HIV infection or positivity on immunoassay. Note: HIV screening test is optional for participants enrolled in the United States, but participants with known HIV infection enrolled in the United States will be excluded.

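### Protocol Table 4: an ANC below 0.5 × 10⁹/L meets both the restart-at-same-dose row and the discontinue row, and no precedence is stated

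*Protocol*

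**What the plan says.** Two adjacent hematology rows of Table 4 in Protocol 6.6.2 matter here.

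- **Interrupt-and-restart row.** Triggers: "ANC ≤ 1.0 × 10⁹/L, unless due to underlying disease" and "Platelet count is 50 × 10⁹/L to < 75 × 10⁹/L, unless due to underlying disease". Drug is held for up to 14 days until recovery to Grade 1 or better, or to the pretherapy level. The second step is "Restart study drug at same dose and monitor as clinically indicated". The row contains no approval step.
- **Discontinue row.** Triggers: "Grade 4 ANC (< 0.5 × 10⁹/L", then "≥ Grade 3 ANC with an oral temperature of at least 38.5°C OR with ≥ Grade 3 infection", then "Platelet count is < 50 × 10⁹/L". The action is "Discontinue study drug administration and follow-up per Protocol. (Exceptions require approval of sponsor".

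The text of 6.6.2 above the table asks for clinical judgment and consultation with the medical monitor on interruptions and reductions. Sections 6.6.3 and 7.1.1 require permanent discontinuation for unacceptable toxicity or harm to the participant, as a matter of judgment and without an ANC figure. Section 9.6 has the Safety Review Committee look regularly at safety data and dose modifications. None of these says which row of Table 4 applies when a value meets both. The SAP does not address the point.

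At entry, exclusion 3 in Protocol 5.2 ("Inadequate hematologic function defined as follows (as determined by local laboratory") bars an ANC below 1.5 × 10⁹/L.

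**The concern.** Both rows stop the drug at once, so the conflict is about what happens after recovery. Under the first row, a participant whose ANC fell below 0.5 and recovered within 14 days goes back on the same dose, so 2.5 mg stays 2.5 mg. Under the second, treatment is over unless the sponsor agrees otherwise. A site that reads the first row literally has a written route to same-dose rechallenge after Grade 4 neutropenia without the approval that the second row demands.

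The platelet lines in the same rows suggest a drafting slip. They carry a lower limit in the restart row and meet the discontinue criterion exactly at 50; only ANC lacks the matching limit.

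There is a small reporting side as well. SAP 8.2.3 summarizes adverse events leading to interruption and those leading to discontinuation in separate tables, so the same clinical event could be counted in different tables depending on which row a site followed.

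**Working it through.** There is no stated figure to reproduce. The check is whether the row criteria, taken as sets of values, overlap. Units are × 10⁹/L, and the ANC values considered are those not due to underlying disease.

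**Step 1: ANC, from the printed limits.**
- Restart row: R = {ANC ≤ 1.0}.
- Discontinue row, first criterion: D1 = {ANC < 0.5}.
- R ∩ D1 = {ANC < 0.5}, which is all of D1.
- On a grid from 0 to 1.50 in steps of 0.01, the values meeting both run from 0.00 to 0.49, which is 50 grid points.

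**Step 2: platelets, as the comparison.**
- Restart row: {50 to < 75}. Discontinue row: {< 50}.
- The intersection is empty. On a grid from 0 to 119 in steps of 1, no value meets both.

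**Step 3: the fever or infection criterion.** Call it D2: ANC of Grade 3 or worse with an oral temperature of at least 38.5°C or an infection of Grade 3 or worse. The restart row has no fever or infection exclusion.
- Grade 4 part: ANC < 0.5 lies inside R, so the overlap is certain.
- Grade 3 part: it overlaps R to the extent that Grade 3 lies within ≤ 1.0. The documents do not print the Grade 3 cut-off, so this part is conditional.

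**Step 4: which row would govern?**

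| ANC, not due to underlying disease | Restart row met | Discontinue row met | Stated precedence |
|---|---|---|---|
| 0.5 to 1.0, no fever or Grade 3 infection | Yes | No | Not needed |
| < 0.5 | Yes | Yes | None |
| Grade 4 with fever or ≥ Grade 3 infection | Yes | Yes | None |
| Grade 3 with fever or ≥ Grade 3 infection | Yes, if Grade 3 lies within ≤ 1.0 | Yes | None |

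An ANC below 0.5 that *is* due to underlying disease meets only the discontinue row, because the exception is printed in the restart row alone.

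**Step 5: could the value simply have been present at entry?** The lowest eligible ANC is 1.5, and 1.5 − 0.5 = 1.0. A value below 0.5 is therefore a fall of more than 1.0 from the eligibility limit. The overlap concerns a new on-study event.

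**Step 6: two possible repairs.**
- *Lower bound plus precedence.* R′ = {0.5 ≤ ANC ≤ 1.0}. R′ ∩ D1 is empty, and R′ ∪ D1 covers every ANC ≤ 1.0, so there is no gap; the grid check agrees. Any remaining overlap of R′ with D2 is settled by the precedence sentence.
- *Lower bound plus a fever or infection exclusion written into the restart row.* If Grade 3 begins below 1.0, or excludes exactly 1.0, a febrile participant between that cut-off and 1.0 would leave the restart row without entering the discontinue row, and so would have no ANC row. The first repair avoids this.

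**The case against.** The strongest reply is that the table resolves the conflict by its structure. The discontinue row names Grade 4 ANC with its cut-off. If the restart row governed below 0.5, that criterion would never operate; reading the rows as steps gives each one a purpose. The catch-all in Table 4 for other Grade 4 toxicity also leads to discontinuation, so stopping at Grade 4 is the table's general pattern. To go wrong, a site would have to pass over the row naming its laboratory value and act without the medical monitor. The table is headed as guidelines, and the Safety Review Committee reviews dose modifications.

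Most of this stands: a sensible reader would discontinue, and the practical effect is limited. It does not remove the defect. The reading is inferred, not stated. The consultation text covers interruptions and reductions and does not name a same-dose restart, which is the step where the rows differ. Consultation is also not approval, and committee review is not stated to come before any given restart.

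Three stronger readings are tempting, and the documents do not support them.
- *That participants would in fact be rechallenged without supervision.* Given the safeguards above, only the written route can be shown.
- *That the size can be given as a percentage*, for example half of the 0 to 1.0 range. That is a share of a number line, not of participants or events. The documents give no neutropenia rate.
- *That the AST/ALT row has the same fault*, because it has no upper limit while other Grade 4 toxicity leads to discontinuation. AST/ALT has its own Chemistry row, and the catch-all sits under a separate heading for other toxicities that does not clearly cover it. The Grade 4 AST/ALT cut-off is not printed, and forcing discontinuation there would be a clinical policy choice.

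**Conclusion.** The point holds for ANC as a low-severity correction to a safety rule. For ANC below 0.5 × 10⁹/L not due to underlying disease, two rows of Table 4 give different instructions on rechallenge, and no text in 6.6.2, 6.6.3, 7.1.1 or 9.6 ranks them. That finding needs only the printed limits. The overlap for Grade 4 ANC with fever or infection is equally certain; the Grade 3 part rests on the assumption that Grade 3 lies within ≤ 1.0. No frequency can be stated, and no endpoint, analysis population, sample size or analysis method is affected. The discontinue row is probably the intended one, so the correction would put the apparent intent in writing and would not change policy.

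**What to change.** Make two edits to Table 4:

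1. Change the ANC trigger of the restart row to ANC 0.5 to 1.0 × 10⁹/L, keeping the underlying-disease exception.
2. Add one sentence: the discontinue row takes precedence whenever any of its criteria is met.

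The first edit gives ANC the same clean split at 0.5 that platelets have at 50. The second settles the fever and infection overlap, whatever the Grade 3 cut-off is, without leaving any ANC ≤ 1.0 not due to underlying disease outside the table.

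The cost is negligible: one altered line and one new sentence, by protocol clarification or in the next amendment, with no new data or visits.

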6.6.3. Criteria for Permanent Discontinuation of Study Drug

The occurrence of unacceptable toxicity not caused by the underlying disease will be presumed to be related to study drug treatment and will require that the study drug be permanently discontinued. Unacceptable toxicity is defined as follows:

• Occurrence of an AE that is related to treatment with the study drug that, in the judgment of the investigator or the sponsor's medical monitor, compromises the participant's ability to continue study-specific procedures or is considered to not be in the participant's best interest.

6.7. Concomitant Medications and Procedures

All concomitant medications and treatments must be recorded in the eCRF. Any prior medication received up to 30 days before the baseline visit will be recorded in the eCRF.

Concomitant treatments and/or procedures that are required to manage a participant's medical condition during the study will also be recorded in the eCRF.

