3. OBJECTIVES AND ENDPOINTS

Objectives	Endpoints					
Primary						
To evaluate the efficacy of INCB050465 in the treatment of participants with AIHA.	• Proportion of participants attaining a CR (defined as hemoglobin >12 g/dL not attributed to transfusion effect* and the normalization of hemolytic markers) at any visit from Week 6 to Week 12.					
	 Proportion of participants attaining a PR (defined as hemoglobin 10-12 g/dL or at least ≥ 2 g/dL increase from baseline not attributed to transfusion effect and the normalization of hemolytic markers) at any visit from Week 6 to Week 12. 					
	*No transfusion effect definition: > 1 week since last transfusion.					
To evaluate the safety of INCB050465 administered as repeat doses in participants with AIHA.	Safety and tolerability will be assessed by monitoring AEs, measuring vital signs and ECGs, and conducting clinical laboratory blood and urine sample assessments.					
Secondary						
To further evaluate the efficacy of INCB050465 in the treatment of participants with AIHA.	 Proportion of participants attaining a CR during postbaseline visits. 					
	Proportion of participants attaining a PR during postbaseline visits.					
	 Proportion of participants attaining a ≥ 2 g/dL increase in hemoglobin from baseline. 					
	Mean, change, and percentage change from baseline of hemoglobin.					
	Proportion of participants requiring transfusions.					
	Proportion of participants who achieve normalization of hemolytic markers. (Hemolysis markers: hemoglobin, haptoglobin, LDH, reticulocyte count, total bilirubin, and direct/indirect bilirubin.)					
	Change of daily usage of prednisone.					
	FACIT-F sub-scale assessment.					
To evaluate the PK effects of INCB050465.	PK endpoints: C _{max} , t _{max} , C _{min} , AUC _{0-t} , and CL/F.					
To evaluate the PD effects of INCB050465.	Change from baseline in PD markers: reticulocyte count, DAT for IgG and C3b, cold agglutinin levels, haptoglobin, total bilirubin, direct/indirect bilirubin, LDH, and complement assessment (CH50, C3, and C4).					

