8.1.4.2. Disease Characteristics and Treatment History

A disease-targeted medical and medication history, including date of diagnosis of AIHA, serological test, rituximab treatment history and other details related to the disease under study, will be collected at screening.

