8.1.5. Prior and Concomitant Medications and Procedures

Prior and concomitant medications and procedures will be reviewed to determine participant eligibility. All concomitant medications and measures must be recorded in the eCRF, and any medication received or procedure performed within screening period before enrollment and up to the end of the follow-up period (see Table 1) will be recorded in the eCRF. The medication record will be maintained after signing the ICF to document concomitant medications, including any changes to the dose or regimen. Concomitant medications include any prescription, overthe-counter, or natural/herbal preparations taken or administered during the study period. Concomitant treatments and/or procedures that are required to manage a participant's medical condition during the study will also be recorded in the eCRF.

Extension Period

Use of concomitant medications should be monitored as described in Table 2 for participants in the extension period of the study to verify that participants are not taking any concomitant medication prohibited per Section 6.7.3.

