6.1.2. Baseline Disease Characteristics

The following baseline disease characteristics will be summarized for the FAS:

- Years since first onset of AIHA (< 2 years, 2-5 years, > 5 years)
- Type of AIHA (warm/cold/mixed type/other)
- Number of hospitalizations due to hemolytic anemia in the past year
- Failed therapies (no/yes [prednisone/rituximab/other])
- Transfusions in the past year (no/yes)
- Splenectomy received (no/yes)

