7.4. Analysis of Secondary Efficacy Parameters

The secondary endpoints include:

1. Proportion of participants attaining a CR during postbaseline visits.
2. Proportion of participants attaining a PR during postbaseline visits.
3. Proportion of participants attaining a ≥ 2 g/dL increase in hemoglobin from baseline.
4. Mean, change, and percentage change from baseline of hemoglobin.
5. Proportion of participants requiring transfusions, defined as "Yes" if the last transfusion is within 7 days of the visit date and "No" otherwise.
6. Proportion of participants who achieve normalization of hemolytic markers (hemolysis markers: hemoglobin, haptoglobin, LDH, reticulocyte count, total bilirubin, and direct/indirect bilirubin).
7. Daily usage of prednisone.
8. FACIT-F subscale assessment.

All secondary endpoints will be summarized using descriptive statistics.

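### The transfusion endpoint is reported in the whole FAS without reference to pre-treatment transfusion status, so participants not transfused before entry are pooled with those who became transfusion-free

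*Protocol*

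**What the plan says.** **Endpoint.** Protocol Section 3 lists, among the secondary efficacy endpoints, "Proportion of participants requiring transfusions". It makes no reference to need before treatment. SAP 7.4 item 5 supplies the rule: "defined as 'Yes' if the last transfusion is within 7 days of the visit date and 'No' otherwise".

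**Analysis set and display.** SAP 5.3.1 puts all efficacy analyses on the FAS, and Table 2.2.5 in SAP Appendix A follows it. SAP 5.2 provides summaries overall and by starting dose regimen. Appendix A lists no table that splits this endpoint by earlier transfusion status, and no shift from baseline is defined for it. The only subgroup analysis described (SAP 7.7) concerns biomarkers, and transfusion status is not among the characteristics it names.

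**Who is enrolled.** Protocol 5.1 asks for hemoglobin between 7 and 10 g/dL. It does not ask for transfusion need. There is no randomization (Protocol 6.4, SAP 3.1) and no control arm.

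**What is recorded before treatment.**
- Protocol 6.7: "Any prior medication received up to 30 days before the baseline visit will be recorded in the eCRF". This sentence is about medication.
- Protocol 8.1.5: "any medication received or procedure performed within screening period before enrollment and up to the end of the follow-up period". Screening lasts up to 28 days.
- Protocol 8.1.4.2: the disease history, with "other details related to the disease under study, will be collected at screening". Transfusions are not named.
- SAP 6.1.2: the baseline item "Transfusions in the past year (no/yes"), summarised for the FAS.

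**The concern.** In an uncontrolled study, the natural reference for transfusion need on treatment is the participant's own need before treatment. The planned proportion drops that reference. A participant who was not being transfused at entry can only stay a No or get worse, yet is counted in the same way as one who came off transfusion.

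The protocol itself thinks in before-and-after terms elsewhere: one of the Cohort 1 dose-increase criteria is that transfusions are still needed by Week 6.

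Two readings of Table 2.2.5 are at stake. A high No share could be taken as benefit when it partly describes who enrolled. A difference between cohorts could be taken as a dose effect when it partly reflects different baseline need. The cohorts have different quotas by AIHA type (Protocol 4.1), so an equal transfusion mix cannot be presumed, although the documents give no transfusion rate by type. SAP 10.1 says the analysis after Week 12 is meant to support publications and a possible Phase 3 plan, so these figures may be read outside the study team.

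**Working it through.** The documents give no figure for this endpoint. The only computed figure in the sample-size sections (Protocol 10.1, SAP 3.3) concerns adverse-event detection at a 20% rate. It reproduces (1 − 0.8^10 = 0.893; 1 − 0.8^15 = 0.965) and has no bearing here.

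**Inputs**
- N = 25 participants: Protocol 10.1.
- k = number with transfusion need before entry: not given; assumed 2 to 18.
- r = share of those k whom the drug frees from transfusion: not given; assumed 0 or 0.5.
- Simplifications: nobody newly needs transfusion, and everyone still in need is a Yes at the visit.

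**Formula**

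No share in the FAS = (N − k + k·r) / N

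| k of 25 | r = 0 | r = 0.5 |
|---|---|---|
| 2 | 23/25 = 92% | 24/25 = 96% |
| 5 | 20/25 = 80% | 22.5/25 = 90% |
| 8 | 17/25 = 68% | 21/25 = 84% |
| 12 | 13/25 = 52% | 19/25 = 76% |
| 18 | 7/25 = 28% | 16/25 = 64% |

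**Reading the table.** A drug that frees nobody gives anything from 28% to 92% No, depending only on k. A drug that frees nobody with k = 5 (80%) also looks better than one that frees half with k = 12 (76%).

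**Same cases, restricted to participants with prior need.** The share freed is k·r/k = r, which is 0% or 50% whatever k is. The baseline mix drops out.

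**How far the simplification carries.** Under SAP 7.4 item 5, a Yes needs a transfusion within 7 days of the visit. From Week 2 the treatment visits are two weeks apart. Between Weeks 6 and 12 the look-backs from Weeks 8, 10 and 12 cover about 3 × 7 = 21 of 42 days. A participant still transfused, but less often than weekly, can be a No at some visits without benefit. That would push the No share above the tabulated values, and would also touch the restricted row. The table shows dependence on k; it does not predict what Table 2.2.5 will report.

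**Precision after a split.** If 0 of k previously transfused participants are still transfused, the upper limit of the exact two-sided 95% interval for the share still transfused is 84% (k = 2), 52% (k = 5), 37% (k = 8) or 26% (k = 12).

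**The case against.** **A stronger reading that fails.** From the 30-day sentence in Protocol 6.7, a reader might infer that transfusions before baseline are not recorded over any usable window. The documents do not support that. The sentence concerns medication and sets no limit on recording transfusions. Protocol 8.1.5 covers both medications and procedures in screening, so a transfusion is covered under either label. SAP 6.1.2 plans past-year status. The response rules in SAP 7.2 need the date of the last transfusion, and Listing 2.2 covers transfusions. The case report form is not among the documents, so it cannot be said that dates or counts of earlier transfusions are missing. The no/yes wording in SAP 6.1.2 describes a summary; it is not a form specification.

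**The size is not known.** A reader might also infer that the proportion mostly reflects who enrolled, or that the cohorts will differ by a stated amount. Neither follows, because k and r are assumed and the 7-day rule is simplified. This objection stands.

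**The endpoint only describes on-study status.** Neither document says that it shows the drug removing the need. That is fair. But it is listed under an efficacy objective in an uncontrolled study, and the table gives no help against that interpretation.

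**The baseline mix will be visible.** Past-year status appears in Table 1.3.1, overall and by cohort. This helps, but two separate margins do not show which participants changed.

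**The analysis is exploratory and the subgroups are small.** Both are true. No hypothesis is tested (Protocol 10.3, SAP 7). This limits the weight of the point without making the pooled proportion easier to interpret.

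**Conclusion.** The concern holds as a point about analysis. Table 2.2.5, as planned, combines two groups for whom a No means different things, and no planned table separates them. It cannot by itself show whether the drug removed the need for transfusion. The past-year item is summarised but not used in this endpoint.

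The conclusion that the proportion depends on baseline mix rests on the SAP rule, the FAS denominator and the entry criteria, and needs no assumed number. The illustrative sizes (80% against 52% No with no drug effect) do rest on assumed inputs and on counting everyone still in need as Yes at the visit.

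The weight is minor to moderate: this is one of eight secondary efficacy items, all descriptive and without p-values.

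**What to change.** Keep the 7-day visit rule in SAP 7.4 item 5. Present Table 2.2.5 overall, as now, and also split by pre-treatment transfusion status, giving counts with denominators for:

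- (a) previously transfused participants who no longer require transfusion;
- (b) previously untransfused participants who newly require it.

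Define the status from data already planned. The preferred source is any transfusion in the screening period (Protocol 8.1.5), with a note that this period varies in length up to 28 days. The past-year item in SAP 6.1.2 is the fallback, with a note that it does not separate remote from current need: one transfusion 11 months earlier counts the same as ongoing dependence. If the case report form already holds dates of earlier transfusions, a fixed, dated window before Day 1 is preferable to either.

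The cost is a sentence in SAP 7.4 and a few table rows, with no new data collection. The downsides are small subgroup denominators, which is why counts should lead, and a percentage that will probably look less favourable than the pooled one.
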